9.3 Carboplatin Dose Modification

Dose modifications for carboplatin are permitted according to the carboplatin prescribing information and local standard-of-care. The following are suggested recommendations for dose modification of carboplatin for hematologic and non-hematologic toxicities.

9.3.1 Hematologic toxicity

At the start of each cycle, the ANC should be $\geq 1500/\text{mm}^3$ and the platelet count should be $\geq 100,000/\text{mm}^3$. Treatment should be delayed for up to 42 days to allow sufficient time for recovery. If the counts have not recovered in 3 weeks, the patient's carboplatin may be dose-reduced, held until adequate neutrophil recovery, or discontinued, according to physician judgment and local standard practice. Growth factors may be used in accordance with American Society of Clinical Oncology (ASCO) and the 2015 NCCN guidelines⁵². Upon recovery, dose adjustments at the start of a subsequent cycle may be made on the basis of the lowest platelet and neutrophil values from the previous cycle (see Table 1).

Table. 1 Carboplatin Dose Modification for Hematologic Toxicities

Toxicity^a	Carboplatin
ANC $< 500/\text{mm}^3$ and platelets $\geq 50,000/\text{mm}^3$	75% of previous dose
Platelets $< 25,000/\text{mm}^3$, regardless of ANC	75% of previous dose
Platelets $< 50,000/\text{mm}^3$, with grade ≥ 2 bleeding regardless of ANC	75% of previous dose
ANC $< 1000/\text{mm}^3$ plus fever of $\geq 38.5^\circ\text{C}$	75% of previous dose

^aNadir prior to cycle

Dose reductions for the first episode of neutropenic fever or thrombocytopenia (platelet count $< 25,000$ or $< 50,000$ with bleeding or that requires transfusion) should be considered permanent.

If a second episode of neutropenic fever or thrombocytopenia requiring dose reduction occurs, the dose of carboplatin should be reduced according to physician judgment and local standard practice. Colony-stimulating factors, such as granulocyte colony-stimulating factor, may be used instead of dose reduction for neutropenic fever or Grade 4 neutropenia according to the local standard practice and ASCO guideline. Patients who require a third dose reduction should be considered for permanent discontinuation of carboplatin.

In the event that dose adjustments are needed for both ANC and platelets, patients should receive the lower dose.

Investigators should be vigilant and alert to early and overt signs of myelosuppression, infection, or febrile neutropenia so that these complications can be promptly and appropriately managed. Patients should be made aware of these signs and encouraged to seek medical attention at the earliest opportunity.

If carboplatin is withheld because of hematologic toxicity, full blood counts (including differential WBC) should be obtained weekly until the counts reach the lower limits for treatment as outlined. The treatment schedule should then proceed in the usual sequence.

No dose reductions are needed for anemia. Patients may be supported per the treating physician's institution's guidelines.

9.3.2 Non-hematologic toxicity

For Grade 3 or 4 non-hematologic toxicities, treatment should be delayed until resolution to less than or equal to the patient's baseline value. Dose reductions at the start of the subsequent cycle should be made on the basis of non-hematologic toxicities from the dose administered in the preceding cycle. **Table 2** provides recommended dose adjustments for non-hematologic toxicities.

Table 2 Carboplatin Dose Modification on the Basis of Non-Hematologic Toxicities in the Preceding Cycle

Toxicity		Adjusted Carboplatin Dose as % of Previous Dose^a
Diarrhea	Grade 3 or 4 ^b	100%
Oral mucositis	Grade 3 or 4	75%
Nausea/vomiting	Grade 3 or 4	75%
Neurotoxicity (motor or sensory)	Grade 2	100%
	Grade 3 or 4	75%
Transaminase elevation	Grade 3	75%
	Grade 4	Discontinue
Other	Grade 3 or 4	75%

AUC= area under the concentration-time curve

^aIf deemed appropriate by the treating physician, adjust carboplatin dose to the specified percentage of the previous AUC

^bOr any grade of diarrhea requiring hospitalization

Nausea and/or vomiting may be controlled with adequate anti-emetics. If Grade 3 or 4 nausea/vomiting occurs despite the use of anti-emetics, the dose may be reduced by 25% for the next course. If tolerated, the dose may be increased back to 100% as soon as possible. If, on Day 1 of any treatment cycle, the patient has oral mucositis, carboplatin may be withheld until the oral mucositis is cleared. If the oral mucositis has not cleared in 3 weeks, carboplatin may be discontinued. If acute Grade 3 oral mucositis occurs at any time, the dose may be given at a 75% dose when the oral mucositis is completely cleared. This may be considered a permanent dose reduction.

9.3.3 Other toxicity

For any Grade 3 or 4 toxicity not mentioned above, carboplatin may be withheld until the patient recovers completely or to Grade 1 toxicity. The treatment may then be resumed at 50% dose. This may be considered a permanent dose reduction. If recovery to Grade 1 toxicity does not occur within 3 weeks, the patient's carboplatin may be discontinued. For Grade 1 and 2 toxicities, no dose reduction should be made.

9.4 Etoposide Dose Modification

Dose modifications for etoposide are permitted according to the etoposide prescribing information and local standard-of-care. Once reduced, the current dose cannot be increased back to 100%. Suggested recommendations for dose modification of etoposide are provided in **Table 3**.

Table 3. Etoposide Dose Modification for Renal Impairment

Creatinine clearance (mL/min)	Etoposide Dose
>50	100%
15-50	75% of dose

9.5 Radiation Dose Modification

We will assess the rate of liver SBRT-specific toxicities in excess of those expected from atezolizumab + chemotherapy. If >3 patients (~20% of projected enrollment) require replacement, enrollment will be paused for the study team to review safety data until that point to assure safe continuation of the study.

Specifically, toxicities of special interest will include those anatomically relevant to the radiation field, including but not limited to: dysfunction, pain, inflammation, obstruction, stenosis, ulceration, perforation, hemorrhage, necrosis, or vasculopathy of the alimentary or hepatopancreaticobiliary tracts. Excess irAEs will also be investigated as possibly related to study combination therapy.

If it is determined that excess toxicity is resulting from the study combination, enrollment may resume at an SBRT dose reduction from 10 to 6 Gy per dose. After dose-reduction, if an additional patient requires replacement due to toxicity, we will again pause enrollment for safety review. An additional dose-reduction to 4 Gy per dose may then be considered. If further toxicity of special interest is observed we will close the study.

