The trials of combination immunotherapy with RT in ES-SCLC are still in early phases and mostly ongoing. In a phase I trial, patients with ES-SCLC who completed induction chemotherapy received 45 Gy of thoracic RT in 15 daily fractions along with pembrolizumab every 3 weeks for up to 16 cycles in a 3+3 dose escalation design. Thirty-three patients completed treatment per protocol with no dose limiting toxicities and few high-grade adverse events. Notably the trial enrolled patients regardless of their response to induction chemotherapy and PD-L1 status. The reported median PFS was 6.1 months and OS was 8.4 months compared to historical results of 4 months PFS and 8 months OS with thoracic RT alone in chemotherapy responders in a phase III trial^{17,37}. Although the clinical benefits are not clear from this trial, a larger study with a homogeneous population is necessary to assess relative efficacy. Several ongoing trials are also evaluating the combination of thoracic RT with anti-CTLA4 and/or anti-PD-1 after induction chemotherapy (NCT03923270, NCT03043599). Additionally there are a few studies under way of immunotherapy with RT in the second line setting (NCT02701400, NCT03262454). Of note, in all of these trials RT has been targeted at thoracic lesions. To our knowledge, no trials with RT targeting metastatic lesions in combination with ICI have been previously done.

Stereotactic radiation therapy for liver metastases

Stereotactic radiation therapy for liver lesions has been well described for both primary hepatocellular carcinoma and metastatic disease³⁸⁻⁴⁰. In a large multi-institutional retrospective series of 427 patients with 568 liver metastatic lesions (from various histologies) treated with SBRT, local control (LC) of the treated lesions was durable. Median duration of local control was 51 months. Small tumors (< 40 cm³) were noted to have improved median local control rates of 52 months, compared to 39 months for tumor volumes \geq 40 cm³. No grade 3 or higher toxicity was reported. The selected dose/fractionation of 30 Gy in 3 fractions in the study has also been shown to be well tolerated⁴⁰. In a phase I dose-escalation study of SBRT for liver metastases, the 30 Gy in 3 fraction regimen shows no grade 3 or higher toxicity⁴¹. This regimen is also an accepted treatment dose for the current SABR-COMET-10 phase III trial analyzing the effect of ablative SBRT in patients with oligometastatic disease⁴².

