6.5.3 Data Collection and Follow-up for Withdrawn Subjects

Every effort should be made to obtain information on patients who withdraw from the study. The primary reason for withdrawal from the study should be documented in the patient's medical records. If a patient requests to be withdrawn from the study, this request must be documented in the source documents and signed by the investigator. Patients who withdraw from the study before on-treatment study effects can be assessed will be replaced. If >3 patients (~20% of projected enrollment) require replacement, enrollment will be paused for the study team to review safety data until that point to assure safe continuation of the study. If it is determined that DLTs of special interest from liver-directed SBRT are occurring at a higher rate than would be expected in previous studies of chemoimmunotherapy and liver-directed SBRT, respectively, we will implement a dose reduction of SBRT as described in Section 9.6 for an additional 3 patients and reassess the rate of toxicity before completing enrollment.

If a patient withdraws from the study, the study staff may use a public information source (e.g., county records) to obtain information about survival status.

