11.2 Treatment Regimen

Induction phase- four cycles of 21 days duration each will be administered as follows:

- Atezolizumab fixed dose of 1200 mg administered IV on day 1
- Carboplatin AUC=5 administered IV on day 1
- Etoposide 100 mg/m² on days 1, 2, and 3 of each cycle
- Stereotactic body radiation therapy administered to up to 3 liver lesions within +/-3 days of cycle 2 day 1.

Maintenance phase: atezolizumab 1200 mg administered on day 1 in 21 day cycles until withdrawal criteria are met as outlined in [**Section 5.5**](#).

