15.2 Analytical Plan

Descriptive statistics will be used to describe all the study endpoints. Mean (standard deviation) and/or median (interquartile range) will be used to summarize the continuous variables. Frequencies and percentages will be used to describe categorical variables.

The primary efficacy analysis will be based on the treated, response-evaluable . All patients who meet eligibility criteria, receive at least one dose of the study drug, and have evaluable 6-month outcomes will be included in the analysis of the primary and secondary endpoints, even if there are subsequent protocol deviations. Patients who withdraw from the study before on-treatment study effects can be assessed will be replaced

Analysis of Primary Endpoints

The 6-month PFS rate and its exact two-sided 95% confidence interval (CI) will be calculated. The primary analysis will be conducted after patients have been on treatment for 6 months. As secondary analysis, we will also evaluate the 6-month PFS as a time-to-event outcome using a non-parametric (Kaplan-Meier) or parametric Weibull model, based on the distribution of the survival function.

Analysis of Secondary Endpoints

The overall survival and progression free survival probabilities will be estimated using Kaplan-Meier method. The median survival and the corresponding 95% CI will also be provided.

**Columbia University Irving Medical Center
Herbert Irving Comprehensive Cancer Center
CUMC IRB – AAAT0174**

The estimates of the overall response rate (ORR), disease control rate (DCR), best overall response (BOR), duration of response, rate of in-field local control and out of field disease progression will be provided with the corresponding 95% CIs.

153 Size/Accrual Rate

The total sample of 18 patients is expected to be accrued over the course of two years (approximately 1 patient/month).

154 Stratification Factors

No stratification factors are applicable to this study.

155 Continuous Monitoring for Toxicity

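### The enrollment pauses in Sections 9.5 and 6.5.3 count replaced patients, so on the natural reading SBRT toxicity in a patient who stays assessable advances neither pause

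*Combined protocol and SAP*

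**What the plan says.** Section 9.5 opens by committing to assess the rate of liver-SBRT toxicity beyond what atezolizumab plus chemotherapy would produce. It lists toxicities of special interest by organ and adds that excess irAEs will be looked into. The number that pauses enrollment is a number of replacements, in the same words in 9.5 and 6.5.3: "If >3 patients (~20% of projected enrollment) require replacement, enrollment will be paused for the study team to review safety data".

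The replacement rule is in 6.5.3 and is repeated in 15.2: "Patients who withdraw from the study before on-treatment study effects can be assessed will be replaced".

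What follows a pause differs between the two sections:

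- **9.5:** if excess toxicity is found, "enrollment may resume at an SBRT dose reduction from 10 to 6 Gy per dose". The second pause follows: "After dose-reduction, if an additional patient requires replacement due to toxicity, we will again pause enrollment for safety review". A step to 4 Gy may then be considered, and further toxicity of special interest closes the study.
- **6.5.3:** a dose reduction for 3 additional patients, then reassessment, if it is determined that "DLTs of special interest from liver-directed SBRT are occurring at a higher rate than would be expected in previous studies". No expected rate is stated. The sentence sends the reader to Section 9.6 for the dose steps, but 9.6 covers overlapping drug toxicities; the steps are in 9.5.

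Separately, Section 15.5 and Table 6 set a boundary on dose-limiting toxicities against an acceptable rate of 30%. The DSMC monitors every treated patient (14.3) and receives SAEs within 24 hours (10.4.5).

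**The concern.** The counted event and the event of interest are different things. SBRT is given at cycle 2: "Stereotactic body radiation therapy administered to up to 3 liver lesions within +/-3 days of cycle 2 day 1". A patient who withdraws in cycle 1, before any radiation, meets the replacement rule and moves the first pause closer. A patient with a serious bowel or biliary event after SBRT who stays in follow-up does not meet it. Section 5.2 keeps patients who stop treatment for toxicity on their scheduled scans, and 6.5.1 lets a patient drop one component and continue the others, so such patients can readily remain assessable.

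The combination has little prior safety data. The background says of SBRT that "the 30 Gy in 3 fraction regimen shows no grade 3 or higher toxicity", but that is SBRT without chemoimmunotherapy. The one series of liver SBRT followed by anti-PD1 therapy that it cites had Grade 3 or higher toxicity in one of five patients. What is at stake is whether the rule meant to catch an SBRT signal would do so before most of the 18 patients have been treated.

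**Working it through.** **1. The plan's own figures.** More than 3 means 4 or more. 3/18 = 16.7% and 4/18 = 22.2%, which bracket the stated figure of about 20%. Exact recursion over Table 6 for n = 1 to 18 gives a crossing probability of 4.6% at a true DLT rate of 30%, within the stated maximum of 5%. Both reproduce.

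**2. What each patient adds to the pauses, reading 6.5.3 and 15.2 as the whole replacement rule.**

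| Patient | First pause | Second pause |
|---|---|---|
| Withdraws in cycle 1, before SBRT, unrelated reason | +1 | 0 |
| SBRT toxicity, stays assessable | 0 | 0 |
| SBRT toxicity, withdraws before assessable | +1 | +1 |

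The second row holds at any toxicity rate and needs no assumption beyond the reading of the rule.

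**3. How many patients could be counted.** Inputs: SBRT at about day 21 (11.2) and an assumed 90-day window, so 21 + 90 = 111 days, or about 3.65 months. Section 15.3 says: "The total sample of 18 patients is expected to be accrued over the course of two years (approximately 1 patient/month").

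- At 1 patient/month, the 18th patient enrolls 17 months after the first. 17 − 3.65 = 13.35, so patients enrolled at months 0 to 13 have complete windows: 14 patients.
- At 18 patients in 24 months (0.75/month, one every 1.33 months), the 18th enrolls at 22.67 months. 22.67 − 3.65 = 19.02, and 19.02/1.33 = 14.3: 15 patients.

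**4. A direct toxicity count with the same cut.** P(X ≥ 4), with X binomial(n, t) and t the assumed true rate of countable SBRT toxicity:

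| t | n = 14 | n = 15 | n = 18 |
|---|---|---|---|
| 10% | 4.4% | 5.6% | 9.8% |
| 20% | 30.2% | 35.2% | 49.9% |
| 30% | 64.5% | 70.3% | 83.5% |
| 40% | 87.6% | 91.0% | 96.7% |

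**5. The contribution of toxicity to the written trigger.** If a fraction f of affected patients is replaced, X is binomial(n, t × f). At f = 0 the probability is 0 for every t. At f = 0.5 it is 4.4% to 9.8% for t = 20% and 14.7% to 28.0% for t = 30% (n = 14 to 18). The documents give neither t nor f. Replacements for other reasons would add to the count, so these figures are not the overall chance of a pause.

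**6. Table 6 as a backstop.** Exact crossing probability over 18 patients, by total DLT rate: 0.5% at 20%, 4.6% at 30%, 19.6% at 40%. Table 6 counts all DLTs, so background events raise the total. With independent background DLTs at assumed rates:

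- SBRT 20%, background 20%: 1 − 0.8 × 0.8 = 36%, crossing 11.9%.
- SBRT 20%, background 30%: 1 − 0.8 × 0.7 = 44%, crossing 29.7%.
- SBRT 30%, background 30%: 1 − 0.7 × 0.7 = 51%, crossing 51.4%.

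**7. Cost of a toxicity-based second pause.** If one such patient is enough, the chance of at least one at a true 10% rate is 1 − 0.9^5 = 41% in 5 further patients and 1 − 0.9^8 = 57% in 8.

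**The case against.** The strongest reply is that the reading is an inference. Nothing limits replacement to the rule in 6.5.3 and 15.2, and 9.5 itself speaks of replacement due to toxicity, so patients with SBRT toxicity might be replaced and so counted. That stands as a limit on certainty. It does not rescue the trigger: no sentence says that a patient with toxicity who stays assessable is replaced, and the first pause would still count withdrawals unrelated to SBRT.

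A second reply is that toxicity is acted on elsewhere. The dose-reduction sentence in 6.5.3 carries no replacement condition of its own, 9.5 can close the study for further toxicity of special interest, Table 6 is checked after each patient, and the DSMC sees SAEs within 24 hours. All true. A reader might therefore infer from this point that the trial has no toxicity stopping rule, or that SBRT toxicity would go unreviewed; the documents support neither. What is missing is narrower: an SBRT-specific number that pauses enrollment.

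Two further cautions stand. It is tempting to set the Table 6 figures at 20% and 30% directly against an SBRT-only rate, but that assumes no background DLTs; Section 4.1.4 reports Grade 3-4 AEs in 67.7% of patients on the chemoimmunotherapy backbone, so the backstop is stronger than that comparison suggests. And the absence of Grade 3 or higher toxicity in the background is not a benchmark for this combination. Whole-regimen monitoring is also defensible where attribution is ambiguous, as 9.6 acknowledges.

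**Conclusion.** The concern holds in a limited form. On the natural reading of the replacement rule, both pauses count an event that SBRT toxicity need not produce, and the first also counts events that SBRT cannot have caused. The logical gap does not depend on any assumed rate: assessable patients with toxicity add zero. Its practical size does. With the same cut and 14 to 18 patients, a direct count would pause with probability 30.2% to 49.9% at a true 20% rate and 64.5% to 83.5% at 30%; the rates and the 90-day window are assumptions. The backstops reduce the consequence but supply no SBRT-specific pause number. This is a cheap safety improvement, not a failure of toxicity monitoring. Confidence is medium because the scope of replacement is inferred.

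**What to change.** Keep the replacement trigger, so that a cluster of early withdrawals still prompts review, and make these changes in both 9.5 and 6.5.3:

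- **First pause:** add a pause when more than 3 SBRT-treated patients have a Grade 3 or higher toxicity of special interest (9.5 list), rated at least possibly related to SBRT, within a fixed window after SBRT (for example 90 days), whether or not they are replaced. The sponsor confirms the grade, window and cut.
- **Second pause:** let it fire when an additional patient has such a toxicity, or requires replacement due to toxicity.
- **Sequence:** state one follow-on sequence in both sections and correct the 9.6 reference in 6.5.3 to 9.5. Keep the dose steps and the review of excess irAEs.
- **Collection:** record these events through the whole window, including after early drug discontinuation or the start of new anti-cancer therapy.

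The cost is mostly wording. AEs are already graded by CTCAE v5.0 and attributed to each therapy (10.3.1, 10.3.2). The collection gap is mainly non-serious Grade 3 events in patients who stop drug early, now followed for 30 days, and events after new anti-cancer therapy, which ends follow-up sooner (10.2). The downside is more review pauses: at a true 10% rate, 4.4% to 9.8% for the first pause, and about 41% in 5 or 57% in 8 further patients for the second. Attribution of some hepatic events will be uncertain.

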9.6 Potential Overlapping Toxicities

**Columbia University Irving Medical Center
Herbert Irving Comprehensive Cancer Center
CUMC IRB – AAAT0174**

The risk of overlapping toxicities between atezolizumab, carboplatin, and etoposide is thought to be minimal. Nevertheless, the attribution and management of certain adverse events that have been associated with each agent separately (e.g., hepatotoxicity, skin and gastrointestinal toxicity) may be ambiguous when the agents are administered together. It is theoretically possible that allergic or inflammatory AEs associated with carboplatin and etoposide (e.g., dermatitis, infusion-associated symptoms) could be exacerbated by the immunostimulatory activity of atezolizumab.

Toxicities should initially be managed according to the recommendations in [**Sections 9.1-9.3**](#) with dose holds and modifications (if applicable) applied to the component of the study drug judged to be the primary cause. For severe (Grade 3) or persistent Grade 1–2 diarrhea, an endoscopic evaluation should be considered. Additional tests, such as autoimmune serology or biopsies, may be used to determine a possible immunogenic etiology for adverse events listed above. If, in the opinion of the investigator, atezolizumab is a potential inciting factor, the dose of atezolizumab may be held for a maximum of 105 days beyond when the next dose should have been given (see [**Section 9.1**](#)). Prompt symptomatic management is appropriate for mild immune-mediated adverse events. In severe cases, immune-mediated toxicities may be acutely managed with systemic corticosteroids or TNF- α inhibitors. These cases should be discussed with the Medical Monitor.

